8.3 Other Secondary Outcomes

The protocol defines a number of secondary endpoints in addition to the two key endpoints described in section 8.2 above. These analyses will be carried out for the final report. Selected secondary endpoints may also be analyzed for interim monitoring reports, to help evaluate the safety and efficacy of the investigational agent.

Below, the secondary outcomes from section 4.2.2 of the protocol are cited, with a short description of the analysis methods. For each outcome, the treatment group comparisons will be stratified by disease severity at study entry and by site pharmacy, as described in section 3 under "stratification".

- Time to discharge for the initial hospitalization. Treatment groups will be compared using time-to-event methods that take into account the competing risk of death, similar to the analyses for time to sustained recovery described in section 8.1.
 - Hospital readmissions will be summarized using methods for recurrent events (i.e. those who are readmitted will re-enter the risk set).⁹
- Days alive outside of a short-term acute care hospital up to day 90. For this analysis, the "last-off" method will be used, i.e., days from the latest hospital discharge to day 90 will be counted. A person who dies within 90 days will be assigned a value of 0, consistent with the approach taken in trials of intensive care-based interventions. We will present

the median days by group and test the hypothesis of no difference between arms with a Wilcoxon rank sum test.

- For interim analyses, only participants who have reached Day 90 (administrative follow-up for those who died) will be included, to avoid bias. Alternatively, a shorter time period may be used.
- Pulmonary+ and pulmonary ordinal outcomes on Days 1-7, and the pulmonary ordinal outcome on Days 14 and 28. The proportion of participants in each category of the pulmonary and pulmonary+ outcomes will be summarized over time (both outcomes at days 1-7, the pulmonary outcome also at Days 14 and 28); at each of those days, treatment groups will be compared using proportional odds models as described in section 3; the proportional odds models will be adjusted for the categories of the pulmonary+ outcome at baseline and for study site pharmacy. If participants in both disease severity strata are enrolled, the models will also be adjusted for the interaction between disease severity stratum and pharmacy.

Additionally, the ordinal outcomes will be dichotomized ("category 1", "best 2 categories" through "best 5 categories"), and proportions will be compared between treatment groups at selected time points using logistic regression. For these analyses, the key dichotomized outcome considers the "best 2 categories", which is similar to the "recovery" outcome in the ACTT-1 trial.

- Clinical organ failure or serious infections, defined by development of any one or more
 of the clinical events listed in Appendix B, through Days 28 and 90. The development of
 organ failure or serious infections will be analyzed as a binary outcome, and the
 proportions of participants who developed organ failure, serious infections or death will
 be compared across arms using stratified CMH tests, overall and for individual
 components.
- A composite of death, clinical organ failure, or serious infection through Days 28 and 90 (see Appendix B). Treatment groups will be compared using standard time-to-event methods, since death is part of the outcome and not a competing risk. (Also described in section 7 as safety analysis).
- Outcomes assessed in other treatment trials of COVID-19 for hospitalized participants in order to facilitate cross-trial comparisons and overviews (e.g. 6-, 7-, and 8-category ordinal scales assessed at Days 1-7, 14 and 28; time to improvement in 1 or 2 categories of ordinal scale; time to best 3 categories of ordinal scale, and binary outcomes defined by improvement or worsening based on other ordinal outcomes). We will try to match the analyses in the other trials, to get results that can be compared. These analyses will not be performed for interim reports to the DSMB, unless requested.
- A composite of cardiovascular events (outcomes listed in items b1, e2 and e3 in Appendix B) and thromboembolic events (item f2). Time to event methods will be used that take into account the competing risk of death, e.g., Gray's test to compare treatment groups.

9 Subgroup Analyses

As stated in the protocol (section 11.2 in version 5.1), subgroup analyses for the primary efficacy outcome (time to sustained recovery) and for important safety outcomes will be performed. The goal is to determine whether and how the treatment effect (active versus control) differs qualitatively across various **subgroups defined at baseline**, and whether there are safety concerns in specific subgroups. Tests for heterogeneity of the treatment effect across subgroups will be carried out.

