 In addition to any grade AEs through Day 7, grade 3 and 4 clinical AEs are being reported through Day 28. The number and percent of participants with incident grade 3 or 4 AEs through Day 28 will be summarized, overall and by system organ class, and compared between treatment groups using stratified CMH tests. (A grade 3 or 4 AE is considered "incident" if the event was not present at baseline or increased to grade 3 or 4 from grades 1 or 2.)

To illustrate the time course, the incidence of *grade 3 or 4 AEs or death* through Day 28 will be summarized by treatment group using Kaplan-Meier estimates of the cumulative incidence functions (CIF).

- Infusion-related reactions and symptoms during infusion or within 2 hours after infusion of the investigational agent or placebo, and infusion cessation prior to completion will be tabulated and compared between treatment groups; analyses are described in section 6.
- Treatment groups will be compared for the proportion of participants who developed *organ failure or serious infections* through Day 28 and through Day 90, overall and by individual components, using stratified CMH tests. Individual components of this composite outcome will be tabulated.
- Treatment groups will be compared for incidence of organ failure, serious infections, or death through Day 28 and through Day 90, using Cox proportional hazards models; cumulative incidence functions will be estimated using Kaplan-Meier estimates.
- Treatment groups will be compared for incidence of a composite of fatal and non-fatal cardiovascular and thromboembolic events, a subset of the organ failure outcome (items 6b1, 6e2, 6e3, and 6f2 in Appendix B). Treatment groups will be compared using Cox proportional hazards models; cumulative proportions of participants with such events will be estimated using Kaplan-Meier estimates.

Comment: Death for causes other than cardiovascular or thromboembolic events is a competing risk. As sensitivity analysis, the treatment groups will be compared using Aalen-Johansen estimates for the cumulative incidence functions and Fine-Gray models to estimate the sub-hazard ratio (investigational agent versus placebo) for the composite outcome. If results differ substantially from the Cox regression and Kaplan-Meier estimates, mortality for reasons other than CVD and thromboembolic events will be investigated in detail.

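### SAP sections 7 and 8.3 disagree on whether death counts in the organ failure or serious infection outcome, and on the main method for the cardiovascular and thromboembolic composite

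*SAP*

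**What the plan says.** **Organ failure or serious infection.** Section 7 (Safety Analyses) states: "Treatment groups will be compared for the proportion of participants who developed *organ failure or serious infections* through Day 28 and through Day 90", by stratified CMH test, overall and by component. Section 8.3 (Other Secondary Outcomes) opens its bullet with "Clinical organ failure or serious infections, defined by development of any one or more" of the Appendix B events, at the same two time points. It says that this will be analysed as a binary outcome, and then that the "proportions of participants who developed organ failure, serious infections or death will" be compared by stratified CMH test, overall and by component. Appendix B lists items a to g, and death is not among them.

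Both sections also have a separate bullet for the composite that does include death. Section 7 has it as a Cox regression bullet: "Treatment groups will be compared for incidence of organ failure, serious infections, or death through Day 28 and through Day 90, using Cox proportional hazards"; section 8.3 has it as the very next bullet, with standard time-to-event methods and a cross-reference to section 7.

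**Cardiovascular and thromboembolic composite.** Both sections build it from Appendix B items b1, e2, e3 and f2. Section 7 says: "Treatment groups will be compared using Cox proportional hazards models; cumulative proportions of participants with such events will be estimated using Kaplan-Meier estimates". A comment there recognises death from other causes as a competing risk and adds Aalen-Johansen and Fine-Gray as sensitivity analyses. Section 8.3 says: "Time to event methods will be used that take into account the competing risk of death", with Gray's test as the example. Section 3 sets the general rule that competing-risk analogues are used when death competes with the outcome.

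**The concern.** The binary comparison in section 8.3 is not of the outcome that its own bullet defines. Read literally, it repeats the next bullet's composite as a proportion, and two results with different numerators could carry the same outcome name. The SAP's other text does not fully settle the point. Section 7 describes the organ failure or serious infection composite as the exempt events listed in Appendix B, but the list of exempt events in Appendix C starts with death, so a programmer could defend either numerator.

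The numerator can matter. In the pooled data on earlier TICO agents (section 9.2), among nAb-positive participants, the hazard ratio was 3.64 for mortality and 1.42 for the composite of death, SAE, organ failure or serious infection. The intervals are wide (1.05 to 12.65 and 0.91 to 2.22), but effects on death and on morbidity need not agree.

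For the cardiovascular composite, two sections each name a different lead analysis and neither says which governs. The two target different quantities: a cause-specific hazard ratio in one, a comparison of cumulative incidence in the other.

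**Working it through.** No sample size, power or event count in the plan depends on this, so there is no stated figure to reproduce. The check is a comparison of the text, followed by two illustrations of size.

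**Step 1: the rules side by side**

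| Item | Section 7 | Section 8.3 |
|---|---|---|
| Organ failure or serious infection: definition | Appendix B, no death | Appendix B, no death |
| Proportion compared | without death | with death |
| Days and test | 28 and 90, stratified CMH | 28 and 90, stratified CMH |
| Separate composite with death | yes (Cox, Kaplan-Meier) | yes (time-to-event) |
| Cardiovascular composite: items | b1, e2, e3, f2 | b1, e2, e3, f2 |
| Fatal and non-fatal stated | yes | no |
| Lead method | Cox, Kaplan-Meier | competing-risk, e.g. Gray's test |
| Competing-risk methods | sensitivity analysis | the stated comparison |

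On death, section 8.3 is the outlier: it departs from section 7, from Appendix B and from the opening of its own bullet. On the cardiovascular method, section 7 is the outlier against section 3. Section 7 itself treats death as a competing risk for the non-pulmonary events of the pulmonary+ outcome.

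Population does not explain the difference for this agent, because Appendix G uses mITT for both efficacy and safety.

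**Step 2: effect of adding death to the proportion**

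Let p be the proportion with an Appendix B event and d the proportion who died. With death added, the proportion lies between max(p, d), when overlap is complete, and p + d, when there is none.

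- MP0420 counts are not given. Assumed d: the AZD7442 figure in Table E-1, 138/1417 = 9.7%.
- Assumed p = 20%: the result lies between 20.0% and 20.0 + 9.7 = 29.7%.
- In numbers of participants, 0.097 × 485 infused = about 47 deaths, of whom only those with no Appendix B event would be reclassified.

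Receipt of high-flow oxygen, non-invasive or invasive ventilation, or ECMO is already an Appendix B event (item a1). Many deaths are therefore likely to have a recorded event, and the shift is probably near the low end.

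**Step 3: Kaplan-Meier against Aalen-Johansen**

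Assume constant cause-specific hazards, 90-day cardiovascular incidence c and other-cause death m. Total cumulative hazard H = −ln(1 − c − m); cardiovascular share h = H × c/(c + m); 1 − KM = 1 − exp(−h). Aalen-Johansen returns c.

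| c | m | 1 − KM | Excess (points) |
|---|---|---|---|
| 3% | 5% | 3.08% | 0.1 |
| 5% | 9.7% | 5.27% | 0.3 |
| 8% | 15% | 8.69% | 0.7 |

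Example: c = 5%, m = 9.7% gives H = 0.159, h = 0.054 and 1 − KM = 5.3%.

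**The case against.** A reader might infer that a mortality difference would end up reported as an organ-failure difference, or would hide one. The documents do not support that. Mortality is a key secondary outcome with its own analysis, the disputed bullet asks for individual components, and section 7 tests the version without death. Any discrepancy would be visible in the full report.

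A reader might also take 9.7 points as the upper limit for this trial. It is not. It comes from another agent's trial, from data as of 28 December 2021; it counts only deaths before recovery; and it concerns Day 90, while the outcome is also compared at Day 28.

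On the cardiovascular composite, a cause-specific Cox model is legitimate. Section 7 names the competing risk, specifies the competing-risk sensitivity analyses, and says that other-cause mortality will be investigated if the results differ substantially. It would be wrong to infer that section 7 ignores the issue or leaves the choice wholly open. The overstatement in Step 3 concerns the Kaplan-Meier proportions, not the Cox comparison.

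One could also argue that a safety section and an efficacy section may each have their own analysis. The text does not say so: only the composite with death is cross-referenced between the sections.

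Finally, section 8.3 takes its outcomes from protocol section 4.2.2, which is not among the documents reviewed, so the direction of the first correction needs a check there. What stands after all this is that two rules in force contradict each other, and that nothing says which governs.

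**Conclusion.** Both inconsistencies are real and are in the current SAP text. The first is an internal contradiction in section 8.3 over whether death counts. Its size for MP0420 is unknown; under the AZD7442 assumption it is between 0 and roughly 10 points at Day 90, probably towards the low end. The second is a conflict over which method leads. Its numerical effect on cumulative proportions is small (about 0.1 to 0.7 points for assumed rates of 3–8% events and 5–15% other-cause death, with constant hazards), and its main effect is on which test and estimand count as the result. Only secondary outcomes are touched. The primary analysis, its alpha and the sample size are unaffected. The point is worth correcting because these are operative analysis rules and the correction is nearly free.

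**What to change.** 1. In the section 8.3 bullet on organ failure or serious infection, delete death from the sentence that states the compared proportions, after checking protocol section 4.2.2. The next bullet already covers the composite with death. One small cost: a participant who dies with no recorded Appendix B event then counts as event-free in the CMH test, so the result should be read beside that composite.
2. For the cardiovascular and thromboembolic composite, estimate cumulative proportions by Aalen-Johansen in both sections.
3. Name one main test for it in both sections. Gray's test follows sections 3 and 8.3; keep the cause-specific Cox hazard ratio as a supporting analysis.
4. Use the same wording in both sections on whether fatal as well as non-fatal events are counted.

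These are wording changes to the SAP and need no new data. Section 1.1 already provides for SAP updates by blinded staff before each agent is unblinded, which is the natural place for them.

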9.1 Outcomes, Subgroups, and Methods

The following outcomes will be considered for subgroup analyses:

- Time to sustained recovery (primary efficacy outcome)
- Time to the composite of *death*, *SAE*, *organ failure*, *or serious infections* through Day 90
- Time to death through Day 28, Day 90, and 18 months
- The composite of grade 3 and 4 events, SAEs, clinical organ failure, serious infections, or death through Day 5 and Day 28
- The Pulmonary and Pulmonary+ ordinal outcomes on Day 5
- Time to discharge from the index hospitalization, an outcome used in other COVID-19 trials.

To support the interpretation of the subgroup analyses for composite outcomes, components of the composites will also be analyzed.

Subgroup analyses will be performed by the following baseline factors:

- Disease severity (categories of the pulmonary+ outcome at study entry, randomization stratum). This subgroup analysis will be used at interim analyses after expansion of enrollment to assess if the treatment effect varies across the severity strata.
- Duration of symptoms prior to enrollment
- Age (18-49, 50-59, 60-69, 70-79, 80+)
- Biological sex
- Race/ethnicity
- Geographic location
- Level of residence (home) at the time COVID-19 symptoms developed
- Baseline pulmonary status (mutually exclusive subgroups: not on supplemental oxygen, supplemental oxygen < 4 L/min, supplemental oxygen > 4 L/min, HFNC or NIV; invasive mechanical ventilation or ECMO)
- Body mass index (BMI)
- History of chronic conditions (cardiovascular disease, diabetes, asthma, chronic obstructive pulmonary disease, hypertension, chronic kidney disease, hepatic impairment, or cancer), and number of chronic conditions (none, 1, 2, 3 or more).
- Plasma antibody status. See section 9.2 below.
- Plasma antigen level. See section 9.2 below.
- SARS-CoV-2 viral RNA level based on midturbinate swab. See section 9.2 below.
- Biomarkers of inflammation and coagulation (including IL-6, hsCRP, and D-dimer)
- Concomitant medications, including subgroups formed by:

- Use of remdesivir prior to study entry (unless contraindicated, participants in both treatment groups were to receive remdesivir up to 10 days as background therapy)
- Use of corticosteroids (4 subgroup categories, formed by the combinations of supplemental oxygen use [yes/no] and corticosteroid use at study entry)

For the AZD7442 investigational agent, additional subgroup analyses will be carried out for the following subgroups defined at baseline; subgroups, hypotheses and analyses are described in Appendix E:

- SARS-CoV-2 vaccination status. Subgroups will be formed by vaccination status and by type of vaccine.
- Immunosuppressive state
- SARS-CoV-2 viral genome sequence and variant lineage.

As a **general rule**, subgroup analyses will be carried out using statistical models that are stratified by disease severity; for time-to-event analyses, stratified Fine-Gray or Cox proportional hazards models will be used, while for other outcomes, models will include the disease severity indicator as covariate. Global tests for heterogeneity of the treatment effect across subgroups will be carried out, by adding the interaction between the subgroup indicator and the treatment group indicator to a model that contains the treatment group indicator and subgroup variable as "main effects". In case the subgroup was formed by categorizing a continuous variable, the models used for the subgroup analyses will contain the (continuous) subgroup variable as covariate, and the interaction term in the expanded model will be formed between the subgroup indicator and the continuous variable.

Subgroup analyses for the primary endpoint of **time to sustained recovery** will use the Fine-Gray model (with death as competing risk), stratified by disease severity at study entry. Within each subgroup, the number and percent of recovered participants and median time to recovery will be calculated by treatment group, and sHRs with 95% CIs comparing the investigational agent versus control will be estimated. Global tests for heterogeneity of the treatment effect across subgroups will be carried out, by adding the interaction between the subgroup indicator and the treatment group indicator to the model that contains data across all subgroups. Median time to recovery will be estimated using Aalen-Johansen estimators.

Subgroup analyses for the **composite safety endpoint at Day 5** will use logistic regression, stratified by disease severity at study entry. Within each subgroup, the number and percent of participants with events will be calculated by treatment group, and ORs with 95% CIs comparing the investigational agent versus control will be estimated. Global tests for heterogeneity of the treatment effect across subgroups will be carried out, by testing for interactions between the treatment group and the subgroup variable in an expanded model, as described above. Additionally, subgroup analyses for the composite safety endpoint **through Day 5** will be conducted using Cox proportional hazards models, stratified by disease severity.

Subgroup analyses for **all-cause mortality** and **safety endpoints** that are analyzed using time-to-event methods (through Day 5, Day 28 and through Day 90) will use stratified Cox proportional hazards models, since death is part of the composite endpoints and not a competing risk. HRs will be estimated with 95% CIs for each subgroup, and global tests of heterogeneity of the treatment effect will be carried out, as described above. The proportional hazards models will be stratified by disease severity.

Subgroup analyses for the **pulmonary** and pulmonary+ ordinal outcomes on Day 5 will use proportional odds models, adjusted for the pulmonary or pulmonary+ category at study entry. In order to summarize the distributions across the categories of the ordinal outcome, the mean score (using 1-7 for best to worst) will be calculated by treatment group within each subgroup. For each subgroup, summary ORs with 95% CIs will be calculated. Global tests for heterogeneity of the treatment effect across subgroups will be carried out, as described above.

Subgroup analyses for **time to discharge from the index hospitalization** will use the Fine-Gray model (with death as competing risk), stratified by disease severity at study entry. Similar analyses as described above for time to sustained recovery will be carried out.

Additionally, subgroup analyses will be conducted for subgroups formed by a disease progression risk score at baseline. The construction of this risk score has been published and will be revisited as data on the sustained recovery endpoint accumulate for new investigational agents.¹⁰

Unless specified otherwise (e.g., the subgroups by nAb status at study entry for AZD7442 described in Appendix E), subgroup analyses will not be adjusted for multiple comparisons. Subgroup analyses will be interpreted with caution due to limited power and uncontrolled type I error.

